14.0 Withdrawal of Subjects

Subjects will be withdrawn from the research without their consent with the occurrence of worsening medical status, medical instability that limits ability to progress mobility or transfer to the ICU. For subjects who request to withdraw from the research trial, investigators may retain and analyze already collected data relating to that subject.

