5.0 Study Endpoints

Physical Performance and Functional Measures: PASS scores & AMPAC scores on evaluation, day three, discharge, and 30-day follow up. Discharge disposition recommended vs ultimate discharge disposition, hospital length of stay, and 30-day readmission. The primary outcome is a change in functional mobility measure- the Postural Assessment Scale for Stroke from PT evaluation to discharge from hospital.

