6.0 Setting

This research will be conducted on the inpatient stroke service at MUSC (ED, 9E, 9W, 8W, ICU) as soon as possible after admission, ideally within the first 24 hours of the patient's admission to the vascular neurology service for an acute stroke. Follow up values will be collected at post discharge neurology clinic (either in person or through password protected zoom call, or doxy.me) by a member of the study team. Adverse events will be documented in the patient's medical chart and research record and the primary investigator will direct and oversee services provided.

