12.0 Outcomes and Analysis

Goal enrollment is 168 participants. Based on the past literature, in similar populations the standard deviation of PASS measurements is at the most 7.20.⁵ Using this, with a sample of 42 patients in each group, with 95% confidence at the end of the study we can estimate this difference within a margin of error of 2.8.

The primary outcome measure will be the change in postural assessment stroke scale scores from time of PT evaluation to hospital discharge. A factorial design will allow for a test of intensity (vs control) and duration (vs control) through pooling across treatment arms. Using the table below, margins (A+C, B+D, A+B, C+D) need to each be 104 given a mean difference of 2.8, standard deviation of 7.2, 80% power and 5% type I error. Given that this is an early phase study, we can increase the type I error to 10% which would decrease the overall sample size needed to 168 patients (42 per arm) whilst still maintaining 80% power.

	Low Intensity	High Intensity	Totals
Low Duration	A	B	A+B
High Duration	C	D	C+D
Totals	A+C	B+D	A+B+C+D

We are planning to conduct the analysis using intention to treat paradigm. In a preliminary analysis we will compute all summary statistics. Initial plots, such as spaghetti plots, will be used to guide our analyses. A general linear mixed model approach will be used to analyze all the outcomes. This model will account for the correlations between time points using either a compound symmetric or spatial structure for the covariance matrix. Post-hoc analyses using Tukey type adjustments will be performed to obtain least squares estimates of the differences between the two randomized groups. Although the study is powered based on only the primary

outcome (PASS), we will apply multiple comparisons adjustments for the rest of the outcomes, using Bonferroni corrections. We will test for the assumptions using diagnostic procedures and take appropriate actions if needed. Also, we will define an outcome to be ‘favorable’ or ‘unfavorable’ based on a threshold and apply generalized linear mixed models with logistic link and repeat the analyses. We will attempt to minimize drop-outs but in case of missing data, we will assume Missing at Random or Missing Completely at Random. If necessary, we will perform multiple imputations. For all analyses, we will use SAS, (MIXED, GLIMMIX, MI and MIANALYZE).

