13.0 Risks, Discomforts and Potential Harms

Early mobilization in the acute stroke population may pose risks including but not limited to falls, decreased cerebral perfusion, worsening weakness and/or worsening stroke. The research team will monitor blood pressures before each PT session to make sure it is safe for the individual to participate. A confidentiality breach is also a risk associated with this research. However, no paper records will be stored or reviewed other than consent forms and only coded data will be used for the analysis. Identifying information will be removed from the primary database. Identifying information will be stored in a separate file with a unique identifier assigned to the patient to link the two datasets.

The PT treatment each participant receives may prove to be less effective or to have more side effects than the other study treatment(s) or other available treatments. The experimental treatments may have unknown side effects. The researchers will inform patients immediately if they learn anything during the course of the study that might make the patient change their mind about participating in the study.

Within the first 24 hours post admission for stroke, ALL patients will be returned to a semi-supine position with the head of bed angle <30-degrees to minimize the risk of decreased cerebral perfusion, which is standard of care. Despite the fact that the treatment group will be seen at an increased frequency for PT services- we will not increase their duration of upright within the first 24 hours of admission, which was thought in the previous AVERT trial to be the cause of poor outcomes. Thus, all patients will participate in PT services but will be placed back in a semi-supine position, less than 30-degrees following upright mobility.

The PI and Co-I's will meet every 25 patients to discuss data and safety monitoring. During these meetings we will look for any negative trends in the data we have collected (vitals, NIH stroke scale- i.e., stroke severity, and functional mobility scores) that could indicate adverse events and provide a timely summary report of adverse events to the IRB/NIH. If at any time, there is an adverse event (i.e.: worsened stroke or death) directly related to PT services at an increased frequency and intensity- the PI and/or Co-I's will alert the IRB immediately.

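### Section 14.0 ends research participation, not only study therapy, on worsening or ICU transfer, with no follow-up planned; this conflicts with intention to treat

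*Combined protocol and SAP*

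**What the plan says.** **Withdrawal.** Section 14.0: "Subjects will be withdrawn from the research without their consent with the occurrence of worsening medical status". The same sentence adds two further triggers: "medical instability that limits ability to progress mobility or transfer to the ICU". The only statement on keeping data concerns a different group: "For subjects who request to withdraw from the research trial, investigators may retain and analyze already collected data relating to that subject".

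**Stopping therapy.** Section 13.0 has a separate rule under which therapy stops when the clinical team judges the patient unstable, documented by a bed-rest order. It does not mention leaving the study.

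**Outcome and analysis.** Section 5.0: "The primary outcome is a change in functional mobility measure- the Postural Assessment Scale for Stroke from PT evaluation to discharge from hospital". Section 9.0 schedules PASS, AMPAC and mRS at evaluation, day three of treatment, discharge and 30 days. Section 12.0: "We are planning to conduct the analysis using intention to treat paradigm". It plans mixed models and says that "in case of missing data, we will assume Missing at Random or Missing Completely at Random", with multiple imputation if necessary. It names no analysis under a missing-not-at-random assumption and gives no dropout allowance.

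**Risk and safety reporting.** Section 13.0 lists the possible risks of early mobilization as including "falls, decreased cerebral perfusion, worsening weakness and/or worsening stroke". Section 6.0 has adverse events entered in the chart and the research record, and Sections 11.0 and 13.0 set out reporting to the IRB. Section 6.0 also lists the ICU among the study locations.

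**The concern.** The triggers in Section 14.0 arise after randomisation, are themselves poor outcomes, and overlap with a named risk of the intervention. A patient withdrawn before discharge has no planned discharge PASS, and none of the planned 30-day PASS, AMPAC, mRS or readmission data. Those values are missing because the patient deteriorated.

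Intention to treat needs outcomes for everyone randomised, in the arm assigned. A rule that stops collecting them on deterioration moves the comparison toward patients who stayed stable. If the arms differ in how often patients worsen, or in how badly withdrawn patients do, the estimate is biased.

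A difference between arms is plausible. The instability trigger is tied to progressing mobility, which the arms attempt at different frequency and difficulty. Section 7.0 makes the study team part of clinical care, and no blinding is described. In Phase I (Section 3.0) the one significant adverse event was in the experimental group, and that patient was removed from the study.

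The safety reviews every 25 patients look for trends in vitals, NIHSS and functional scores. Withdrawal would end those data for the patients most likely to show a trend.

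**Working it through.** **1. Do the sections fit together?**
- Section 14.0 ends research participation; Section 13.0 ends therapy only. They are distinct rules, so Section 14.0 cannot be read as merely stopping therapy.
- The retention sentence in Section 14.0 covers patients who ask to leave. For those withdrawn by the investigator, neither retention nor follow-up is stated.
- Between evaluation and discharge the only scheduled scores are at day three. A patient who worsens before then leaves only the evaluation score. Missing completely at random is untenable. Missing at random would need the observed scores to explain the deterioration, which is doubtful, most of all when it comes early.

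**2. The plan's sample size (Section 12.0: difference 2.8, SD 7.2, 80% power).** Normal approximation, two-sided (sidedness is not stated, but two-sided reproduces the figures):

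n per margin = 2 × (z for alpha + z for power)² × (SD / difference)²

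- Alpha 5%: 2 × (1.960 + 0.842)² × (7.2/2.8)² = 103.8, so 104 (stated: 104).
- Alpha 10%: 2 × (1.645 + 0.842)² × (7.2/2.8)² = 81.8, so 82 per margin and 164 in total (stated: 168, or 84 per margin).

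**3. Power if patients have no discharge PASS.** Power = Φ(2.8 / (7.2 × √(2/n)) − 1.645). The loss rates are assumed, spread evenly over the margins, and lost patients contribute nothing.

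| Loss | n per margin | Power |
|---|---|---|
| 0% | 84 | 80.9% |
| 5% | 79.8 | 79.1% |
| 10% | 75.6 | 77.2% |

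**4. Illustration of bias on the planned comparison.** The documents give no worsening rates, so every input is assumed: mean PASS change -6 if worsened and +3 if not, in every arm, and one worsening rate shared by the three active arms. The test pools arms, so the low-intensity margin (A + C) contains control and one active arm, and the high-intensity margin (B + D) contains two active arms. A margin's mean change is 3 − 9 × (its worsening rate).

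- Control 5%, active 10%: the margins are (5% + 10%)/2 = 7.5% and 10%. Means are 2.325 and 2.100; true difference -0.225.
- Control 5%, active 15%: the margins are 10% and 15%. Means are 2.10 and 1.65; true difference -0.45.
- If withdrawn patients are excluded, both margins show +3, a difference of 0.

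The other factor gives the same numbers by symmetry. The arm pattern matters: with rates of 5% (A), 10% (B), 10% (C) and 15% (D), the margins are 7.5% and 12.5% and the difference is 9 × -0.05 = -0.45. With equal rates and an equal gap in outcome, there is no bias.

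**The case against.** A reader might infer more than the documents support, in four ways.

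- **That Section 14.0 deletes the harms.** It does not. The triggering event is recorded under Section 6.0, and reported or summarised under Sections 11.0 and 13.0. The Phase I patient was removed, yet the event was reported. What is at risk is outcomes and harms after withdrawal.
- **That worsened patients drop out of the primary analysis altogether.** No section says so. If their earlier scores are kept, a mixed model or imputation can use them, so the exclusion in the illustration is a limiting case. Retention may also be covered in the consent form, which was not available for this review. Even so, earlier scores do not replace a discharge PASS, and the document plans no follow-up.
- **That missing at random fails by design, with bias toward the active arms.** Missing at random allows missingness to depend on observed data, and evaluation and day-three scores may capture some of the decline. The assumption is doubtful, not refuted. Direction depends on rates and outcomes by arm, which are not given.
- **That listing the ICU as a setting contradicts withdrawal on ICU transfer.** A stable patient enrolled in the ICU satisfies both, since transfer suggests later escalation. This needs clarifying, no more.

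It is also fair to say that 30-day assessment of deteriorated patients takes effort. The visit is already scheduled and may be virtual.

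**Conclusion.** The point stands in this form: Section 14.0 ends research participation on worsening, instability or ICU transfer, with no stated follow-up or data retention, and this conflicts with the intention-to-treat plan in Section 12.0. It affects the primary outcome, the 30-day outcomes and the detection of later harms. That conclusion rests on the text alone.

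The size of the bias is not known. The values of -0.225 and -0.45 PASS points, set against a design difference of 2.8, only show how a deficit could disappear under assumed inputs and full exclusion. They do not estimate what will happen in this trial. The power figures need only an assumed loss rate: the design has less than one percentage point above 80%, and a 5% loss uses it up.

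Follow-up not collected during the trial may not be recoverable, so the rule should be changed rather than handled at analysis.

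**What to change.** - **Reword Section 14.0.** State that these events may end study therapy under the existing clinical rule, which is left unchanged, while the patient remains in follow-up. Only withdrawal of consent ends data collection.
- **Collect and analyse.** Obtain discharge and 30-day PASS, AMPAC and mRS, length of stay, readmission and adverse events wherever possible, and analyse them in the randomised arm.
- **Retention.** State that data already collected from these patients are kept.
- **Section 12.0.** Add one missing-not-at-random sensitivity analysis, for example with delta-shifted scores, for patients with no discharge PASS after worsening or death.
- **Section 6.0.** Clarify how ICU transfer as a withdrawal trigger fits with the ICU as a study setting.

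The cost is small: a reworded paragraph, a clarification, one extra analysis, and some 30-day assessments of deteriorated patients in clinic or virtually, as already scheduled.

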15.0 Potential Benefits

The potential benefit to patient's is that the treatment they receive may prove to be more effective than the other study treatment or than other available treatments, although this cannot be guaranteed. Certain treatment arms may increase a patient's independence and may lead to a shorter hospital length of stay and improved functional mobility outcomes (i.e.: regaining the ability to stand and walk).

It is hoped that the information gained from the study will help in the treatment of future patients with similar conditions and that it will help the researcher learn more about physical therapy approach to mobility post stroke.

15.0 Sharing of results with subjects:

Results of the study will not be shared with the individual subjects

16.0 Significance

The Department of Physical Therapy in conjunction with the Comprehensive Stroke Center at the Medical University of South Carolina (MUSC) seeks support for developing an evidence-based approach for the mobilization of patients within the first 24 hours after an acute stroke admission and for increasing the frequency and intensity of acute PT services while inpatient. This evidence will prepare physical therapists and guide the practice in the delivery of acute stroke mobilization in the hospital setting to optimize length of stay, disposition planning, and enhance long term recovery outcomes. As a comprehensive stroke center, MUSC strives to provide the best of patient care by committing to a higher standard of clinical service, providing a framework to improve patient outcomes, and organizing teams within the continuum of care-

therapy included. A cohesive approach to mobilization in the hyper acute phase of stroke may impact patient outcomes across the continuum of care.

The critical barrier to progress of our current knowledge is the lack of implementation of randomized controlled therapy trials in the hospital setting. Funding from the Acute Care Research grant for salary support, patient treatment costs and supportive personnel will allow us to address these very important questions regarding the appropriate PT approach to patients admitted to the hospital with a stroke. It is an honor to be a practicing clinician who is provided with the support and ability to partake in the research that shapes our field. The proposed project has completed a successful Phase I which demonstrated improved functional gains with increased frequency and intensity of therapy services post stroke. The evaluation of these early, intense and frequent therapy services with an acknowledgement of the importance of cerebral perfusion will assist in developing the interventions that will drive the hyperacute field of neurorehabilitation.

References

1. Verheyden, Geert, et al. "Trunk performance after stroke: an eye-catching predictor of functional outcome." *Journal of Neurology, Neurosurgery & Psychiatry* 78.7 (2007): 694-698.
2. Morgan, Prue. "The relationship between sitting balance and mobility outcome in stroke." *Australian Journal of Physiotherapy* 40.2 (1994): 91-96.
